- h. Subjects will receive two MRI scans, one before and one during the administration of ketamine. MRI scans will be performed at the NYSPI MRI facility using the 3.0 Tesla GE scanner. The first measurement will consist of quantitative MRI imaging for optimal segmentation of brain tissue into gray and white matter and cerebrospinal fluid. The second measurement will be the MR spectroscopy acquisition with GABA and glutamate spectroscopic editing. Patients will receive a structural and spectroscopy MRI scan lasting approximately 90 minutes. Structural scans will include T1-weighted images.

i. Optional 2nd Ketamine Infusion for Non-Responders:

a. The ketamine response will be assessed on Days 1 and 3. Patients who maintain their non-responder status by Day 3 (defined as less than a 50% improvement in their HDRS score) following the ketamine/placebo infusion, will have the option of completing a second ketamine infusion in the Biological Studies Unit of 0.5 mg/kg, if the ketamine dose they received during the first scan was below 0.5 mg/kg. Non-responders who received 0.5mg/kg of ketamine during the first scan and who experienced no psychomimetic or cardiovascular effects requiring intervention will have the option of completing a second ketamine infusion in the Biological Studies Unit of 0.7mg/kg. However, if the patient becomes a responder at any point prior to the scheduled date of the optional 2nd scan/ketamine infusion, the 2nd ketamine infusion will be cancelled.

ii. Randomization and Partial Unblinding Process:

- a. The study statistician performs the randomization and a physician (not involved in patient's treatment or post-ketamine ratings) will write the drug order.
- b. The physician responsible for writing the drug order will also complete a form indicating the eligibility based on the randomization assignment as either 0.5 mg/kg of ketamine or less (note: the other dose will not be specified so that partial blinding is maintained.) This form will be placed in a sealed envelope to be opened only for patients who are found to be non-responders.
- c. In the event that a subject remains a non-responder by Day 3, the treating physician, following the completion of the study ratings, will open the envelope to determine if the patient is eligible for the 2nd ketamine infusion of 0.5 mg/kg or 0.7mg/kg.
- d. The second infusion will take place at the soonest possible date, within 1 week of the first infusion/MRI.
- e. In the event that a patient elects to undergo a second ketamine infusion, the procedures will be consistent with the first infusion/MRI with the following exceptions:

i. The ketamine dose administered will be open-label 0.5 mg/kg or 0.7mg/kg.

ii. No blood samples will be drawn post-infusion. iii. No MRI scan will be conducted. The infusion will be administered under the supervision of a medical doctor and nurse in the Biological Studies Unit, following all non-MRI related safety protocols of the first infusion/scan.

6. Safety Follow-up for Ketamine Abuse/Use Follow-up:

- a. On dates equivalent to Day 1, 3 and 7, and weeks 6 and 12 post infusion, the clinician will evaluate patients using the HDRS-24, CGI, C-SSRS, BDI, and POMS and patients will complete the QIDS-SR to assess an intent-to-treat sample.
- b. At 3 and 6 months post-ketamine, all subjects we can contact will be evaluated to determine the absence of post-exposure ketamine use/abuse.
- c. For those subjects that undergo a second or third ketamine infusion and MRI scan, they will complete a day 1, 3, and 7 follow-up for each scan, and follow-up timepoints at week 6, and months 3 and 6 will follow the final MRI scan.
- d. Outside of the mandatory follow-ups, for those who elect to take advantage of the open treatment offered, visits will occur at least every 2 weeks prior to response, and a minimum of once a month following response.

7. Withdrawal from Study:

Subjects will be withdrawn from the study if:

- a. They request it for any reason
- b. The PI judges that it is medically unwise to continue in the study, for example if the subjects are unable to comply with the study procedures and rules.
- c. They are unable to tolerate the medication washout because of pronounced worsening of symptoms such as marked agitation, inability to drink fluids, suicidal behavior or suicidal ideation with a plan or intent.
- d. A rise in systolic blood pressure \geq 200 mm Hg or diastolic blood pressure to \geq 115 mm Hg during the ketamine infusion.

e. Other criteria for discontinuation will be appearance of psychosis, new suicidal ideation, mania, severe agitation, or other deterioration where the treating physician decides that a change in treatment or hospitalization is indicated.

Healthy Volunteers:

1. Screening:

- a. Subject responds to advertisement and completes a phone screen, approved under IRB #6879R-#5880R. If the subject appears eligible based on the phone screen, they will be scheduled for an in-person screening visit under Screening Protocol (IRB #6879R-#5880R) to determine whether inclusion/exclusion criteria (excluding medical screening) are met.
- b. Subject is given a detailed, verbal explanation of this study (IRB #6460) and IRB #4815 and given a copy of both consent forms.
- c. Subject gives written informed consent to participate in IRB #4815 and IRB #6460.
- d. Subject receives medical evaluation under IRB #4815 and an ECG under IRB #6460 to rule out exclusionary medical illnesses.
- e. At screening, subjects will complete the MADRS.

2. MRS and MRI Scanning:

_

- a. Subject will be informed that they should arrive to the clinic fasting (12 hours no food, 4 hours no liquids) prior to the ketamine infusion/MRI.
- b. We will obtain MRI scans before, and during, a slow intravenous infusion of saline solution with 0.5 mg/kg of ketamine hydrochloride (Abbott Laboratories, North Chicago, IL) over the course of approximately 40 minutes (see Figure 1).
- c. To avoid multiple sticks drawing the blood samples for ketamine, norketamine and GABA at 90 minutes and 120 minutes after the start of the ketamine infusion, a second venous line will be placed.

- d. During the ketamine infusion, vital signs (blood pressure and heart rate) will be monitored as follows:
 - i. -5 minutes
 - ii. 0 (start of infusion)
 - iii. Post start of infusion: 5, 10, 15, 20, 25, 30, 35, and 40 minutes (end of infusion)
 - iv. Post end of infusion:
 - 1. Every 5 minutes for remaining duration of the scan.
 - 2. Blood pressure will continue to be obtained until there are two measurements at least 15 minutes apart that are within normal range or 10 mmHg of the baseline diastolic blood pressure or diastolic blood pressure is at least below 85.

During the ketamine infusion and MRI scans, the vital signs are obtained by an In Vivo® machine which displays in the room with the MRI scanner and physician who supervises the patient's medical state, and also displays in the operator's room on another console (where notes can be taken). The Research Assistant who remains in the operator's room during the infusion records the blood pressure and heart rate. After the subject is transferred back to the examination room, the blood pressure and heart rate will be obtained manually by the research assistant or nurse.

- e. Intervention for Hypertension: Same as above for patients.
- f. If high blood pressure is symptomatic, i.e., blurred vision, headache, chest pain, the subject will be transferred to the ER.
- g. Subjects will receive two MRI scans, one before and one during the administration of ketamine. MRI scans will be performed at the NYSPI MRI facility using the 3.0 Tesla GE scanner. The first measurement will consist of quantitative, structural MRI imaging for optimal segmentation of brain tissue into gray and white matter and cerebrospinal fluid. The second measurement will be the MR spectroscopy acquisition with GABA and glutamate spectroscopic editing. Patients will receive a structural and spectroscopy MRI scan lasting approximately 90 minutes. Structural scans will include T1-weighted images.

3. Follow up: At 3 and 6 months post-ketamine, all subjects we can contact will be evaluated to determine the absence of post-exposure ketamine use/abuse.

4. Withdrawal from Study:

_

Subjects will be withdrawn from the study if:

- a. They request it for any reason
- b. The PI judges that it is unwise to continue in the study, for example if the subjects are unable to comply with the study procedures and rules.
- c. A rise in systolic blood pressure \geq 200 mm Hg or diastolic blood pressure to \geq 115 mm Hg during the ketamine infusion.
- d. Other criteria for discontinuation will be appearance of symptoms meeting criteria for a psychiatric disorder according to DSM-IV criteria.

You can upload charts or diagrams if any

Criteria for Early Discontinuation

Criteria for Early Discontinuation

MDD Patients

Subjects will be withdrawn from the study if:

- a. They request it for any reason
- b. The PI judges that it is medically unwise to continue in the study, for example if the subjects are unable to comply with the study procedures and rules.
- c. They are unable to tolerate the medication washout because of pronounced worsening of symptoms such as marked agitation, inability to drink fluids, suicidal behavior or suicidal ideation with a plan or intent.

- d. A rise in systolic blood pressure \geq 200 mm Hg or diastolic blood pressure to \geq 115 mm Hg during the ketamine infusion.
- e. Other criteria for discontinuation will be appearance of psychosis, new suicidal ideation, mania, severe agitation, or other deterioration where the treating physician decides that a change in treatment or hospitalization is indicated

Healthy Controls

Subjects will be withdrawn from the study if:

- a. They request it for any reason
- b. The PI judges that it is unwise to continue in the study, for example if the subjects are unable to comply with the study procedures and rules.
- c. A rise in systolic blood pressure \geq 200 mm Hg or diastolic blood pressure to \geq 115 mm Hg during the ketamine infusion.
- d. Other criteria for discontinuation will be appearance of symptoms meeting criteria for a psychiatric disorder according to DSM-IV criteria.

Blood and other Biological Samples

Please create or insert a table describing the proposed collection of blood or other biological specimens a) Protocol # 4815: Medical screening and genetics: 59 mL

b) MRI/MRS Scans: Venous line samples will be used to measure blood levels of ketamine, norketamine and plasma GABA at 90 min and 120 minutes after the start of the infusion: (2 X 16 mL for one MRI/infusion)

c) Total for MDD Responders to MRI/infusion: 91 mL

Total for Healthy Volunteers: 91 mL

Assessment Instruments

Create a table or give a brief description of the instruments that will be used for assessment

	Maximum	Screening	Pre-MRI Scan	At about 80, 95, 110 Min Post	~230 Min	Follow up
	Time		Scan	Start of Infusion	Post Start of Infusion	Days 1, 3 & 7, Weeks 6 & 12
	(Mins)					(Month 3) ^a
Applies to (Patients/Controls)		Both	Both	Both	Both	Patients
Hamilton Depression Rating Scale-24	10		X			X
Hamilton Depression Rating Scale-18	10				X	
The Profile of Mood States (POMS)	1		X	X	X	X

Beck Depression Inventory	10		X		X	X
Brief Psychiatric Rating Scale I	10		X		X	
MADRS	10	X				
C-SSRS	15	X	X		X	X
QIDS-SR	5					X
Clinical Global Impressions (CGI)	1					X
Total Maximum Time (Min)		25	46	1	46	42

a. For those subjects that undergo a second or third ketamine infusion and MRI scan, they will complete a day 1, 3, and 7 follow-up for each scan unless superseded by the following MRI scan/infusion, and follow-up timepoints at week 6 and months 3 follow the final MRI scan. Please attach copies, unless standard instruments are used

Off label and investigational use of drugs/devices

Choose from the following that will be applicable to your study

✓ Drug

Select the number of drugs used in this study

Drug #1

Name of the drug
Ketamine
Manufacturer and other information
JHP Pharmaceuticals (Ketalar)
Approval Status
No IND is required
Choose one of the following options
FDA has determined that IND is not required

Research Related Delay to Treatment

Will research procedures result in a delay to treatment?

Yes

Maximum duration of delay to any treatment

For depressed patients who are on medications that may interfere with the study when identified, other than: neuroleptics (1 month), fluoxetine (6 weeks), and serotonin-depleting drugs (3 months) (see inclusion criterion #5), the delay will not exceed 30 days (one week taper, two weeks drug-free, and one week to schedule and complete biological testing). The 30-day period takes into consideration all types of medications, tapering requirements, the drug-free period and the time required for all biological testing.

Protocol Summary Form 6460 [name]

The exclusion above, of neuroleptics, fluoxetine, and serotonin-depleting drugs prior to participation will remain, but we will only include patients whose recent use of these drugs have already been terminated several weeks prior to their presentation to the investigators so that no individual should need to be maintained off medication more than 30 days before the administration of the research medication. Maximum duration of delay to standard care or treatment of known efficacy

We expect that both the first and second ketamine infusion will be conducted within the 30-day time frame described above. We will reserve standing MRI slots to help make this possible.

The maximum delay before initiating treatment of known efficacy will be 50 days. This 40-day time period includes the maximum delay preceding the second ketamine infusion for initial non-responders (37 days), an additional 3 days after the second ketamine infusion when response will be assessed.

Treatment to be provided at the end of the study

After study completion, patients will be offered up to six months of outpatient medication treatment or up to 8 weeks of inpatient treatment or combination of inpatient and outpatient treatment in the Division of Molecular Imaging and Neuropathology clinic. Subjects who are unable to tolerate the medication washout have the option of remaining in open treatment with their assigned MIND physician for up to 6 months.

Clinical Treatment Alternatives

Clinical treatment alternatives

This is a study of intravenous ketamine in the treatment of MDE. A variety of different pharmacological (e.g. selective serotonin reuptake inhibitors, noradrenergic and dopaminergic medications, monoamine oxidase inhibitors and tricyclic antidepressants), psychotherapeutic, electroconvulsive and other therapies are available for MDE.

Risks/Discomforts/Inconveniences

Risks that could be encountered during the study period

Risks associated with participation in this study are related to 1) drug-free interval, 2) side effects of intravenous ketamine, 3) intravenous catheters, 4) blood sampling, 5) MRI scanning, 6) pregnancy, and 7) electrocardiogram.

Describe procedures for minimizing risks

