To study the relationship between Glu/GABAergic response and the degree of clinical improvement at various time points after the ketamine infusion, we will employ a doubleblind, placebo-controlled study with several different doses of ketamine and placebo. This design will establish a dose-response curve between ketamine dose, clinical response, and Glu/GABA response on MRS. The use of different doses of ketamine is expected to increase the variance in the degree of clinical improvement and therefore the ability to detect a relationship to Glu/GABA responses.

Specific Aims and Hypotheses

Specific Aims and Hypotheses

Primary hypotheses.

Aim 1: We hypothesize that administration of ketamine in drug-free MDD will induce a dose-dependent reduction in the 24-item Hamilton Depression Rating Scale (HDRS-24) scores of these patients. This hypothesis will be tested within a linear model with change in HDRS score as response, dose as predictor, and other clinical and demographic covariates included as appropriate.

Aim 2: We hypothesize that administration of ketamine in drug-free MDD will induce a dose-dependent increase in glutamate levels measured with 1H MRS. This hypothesis will be tested within a linear model

with change in glutamate level as response, dose as predictor, and other clinical and demographic covariates included as appropriate.

Aim 3: We hypothesize that administration of ketamine in drug-free MDD will induce a dose-dependent increase in GABA levels measured with 1H MRS. This hypothesis will be tested within a linear model with change in GABA level as response, dose as predictor, and other clinical and demographic covariates included as appropriate.

Aim 4: We hypothesize that the magnitude of the glutamate and GABA responses to ketamine in the same MDD sample as in Aim 1 will correlate with the degree of improvement on the 24-item Hamilton Depression Rating Scale (HDRS-24) from baseline to 24 hours after ketamine infusion. This hypothesis will be tested using partial correlation analysis, i.e., determining the correlation between change in HDRS score and change in glutamate and GABA levels.

Exploratory Aims

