- b. In cases where a subject becomes too unstable during the taper or medication-free phase, as assessed by the research and/or inpatient clinical teams, to wait for the MRI session, then open clinical treatment will be initiated. If a participant is unable to do the MRI scan for any reason, then they will be dropped from the study and given open clinical treatment. Because the possible medication regimens that patients are on are myriad, it is difficult to operationalize the taper process further. For patients who require hospitalization because of destabilization or suicidal risk, admission to the NYSPI unit will be available. Hospitalized patients will be discharged from the hospital when stable as judged by the inpatient staff and the treating psychiatrist as not being in imminent risk of harm to self/other.

c. Emergency Procedures.

i. A research psychiatrist will be available by cellphone 24 hours a day, seven days a week. Patients requiring urgent admission will be brought to the CUMC Emergency Dept. by the study physician with security assistance, if

needed. Non-emergent admissions will be arranged by the treating psychiatrist, if possible to the 4-Center or 5-South. Patients who are deemed to require hospitalization, but who refuse, will receive all necessary interventions such as contacting the local crisis team, family, or Emergency Medical Services.

5. MRS and MRI Scanning:

- a. Subjects will be informed that they should arrive to the clinic fasting (12 hours no food, 4 hours no liquids) prior to the ketamine infusion/MRI.
- b. We will obtain MRI scans before and during a slow intravenous infusion of saline solution with ketamine hydrochloride (Abbott Laboratories, North Chicago, IL) over the course of approximately 40 minutes (see Figure 1).
- c. Ketamine dosing:
 - i. Patients will be assigned to one of five ketamine doses or placebo, as detailed in Figure 2 (p. 11).
 - ii. Randomization will be performed by the study statistician, who will assign MDD participants to randomized treatment in two strata (chronic and non-chronic). Because chronicity of depression has been strongly associated with relapse after antidepressant treatment in previous studies, participants will be stratified according to chronicity. "Chronic" will be defined as current episode of major depressive disorder ≥ 2 years; all others will be "non-chronic."

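### Aims 1–3 model change scores on dose without committing to adjust for the pre-infusion value of the outcome, which can cost precision in a sample well short of target

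*Protocol*

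**What the plan says.** Protocol, Specific Aims and Hypotheses, gives the three primary dose hypotheses one model form.

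- Aim 1: "This hypothesis will be tested within a linear model with change in HDRS score as response, dose as predictor", followed by "and other clinical and demographic covariates included as appropriate".
- Aim 2: a linear model "with change in glutamate level as response, dose as predictor, and other clinical and demographic covariates included as appropriate".
- Aim 3: the same, "with change in GABA level as response, dose as predictor, and other clinical and demographic covariates included as appropriate".

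None of the three names the pre-infusion value of its outcome as a covariate, and none rules it out.

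Those values are part of the planned data. The table under Assessment Instruments schedules the "Hamilton Depression Rating Scale-24" at the pre-MRI visit. Study Procedures, Patients, item 5h, states: "Subjects will receive two MRI scans, one before and one during the administration of ketamine". On allocation, item 5c of the same section says: "Patients will be assigned to one of five ketamine doses or placebo". The ratio is in Figure 2, which is not reproduced in the text at hand.

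On numbers, Description of Subject Population requires 76 MDD completers from a projected 120 enrolled. The continuation report at the front records 57 MDD patients and 13 healthy volunteers enrolled and 42 completers in all, without a split by group. It also says that interventions are finished and only analysis remains.

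**The concern.** A change score with no baseline term fixes the coefficient of the baseline value at 1. If the true coefficient differs from 1, two things follow. The residual variance is larger than it need be. And any chance association between dose and baseline in the patients actually randomised passes into the estimated dose slope through regression to the mean.

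Both matter more in a small sample. Recruitment has ended below target, so the analysis model is the main means left to recover precision for three primary tests. The covariate clause allows adjustment but does not promise it. It also fits Aims 2 and 3 poorly, because pre-infusion glutamate and GABA are imaging measures, not obviously clinical or demographic ones. Leaving the choice open while analysis is under way also means that the reported model could depend on which version was preferred after the data were seen.

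**Working it through.** **The plan's own figure.** The 76 required completers cannot be reproduced: the Protocol states no alpha, power, effect size, SD or pre–post correlation.

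**Sample available.** 42/76 = 55% of target if all 42 completers are MDD patients. If all 13 healthy volunteers completed, 42 − 13 = 29 MDD completers remain, and 29/76 = 38%. Over six groups that is 29/6 ≈ 5 to 42/6 = 7 per group, on the assumption of equal allocation.

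**Residual variances.** Let s0 and s1 be the baseline and follow-up SDs within a dose group and r their correlation.

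- Change score: s0² + s1² − 2·r·s0·s1
- Baseline-adjusted: s1²·(1 − r²)
- Difference: (s0 − r·s1)², which is never negative

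So adjustment cannot raise the residual variance, and it gains nothing only when s0 = r·s1. That is also the case in which the true baseline coefficient, r·s1/s0, equals 1 and chance imbalance does no harm to the change-score slope.

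**Ratio of adjusted to change-score variance.** With s0 = s1 it reduces to (1 − r²)/(2(1 − r)) = (1 + r)/2. In general, with k = s1/s0, it is k²(1 − r²)/(1 + k² − 2rk). All values of r and k here are assumptions.

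| r | k = 1 | k = 1.5 | k = 2 |
|---|---|---|---|
| 0.3 | 0.65 | 0.87 | 0.96 |
| 0.5 | 0.75 | 0.96 | 1.00 |
| 0.7 | 0.85 | 1.00 | 0.93 |
| 0.9 | 0.95 | 0.78 | 0.54 |

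Example: k = 1.5, r = 0.5 gives 2.25 × 0.75/(3.25 − 1.5) = 1.6875/1.75 = 0.96.

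For k = 1, omitting baseline inflates the residual variance by 1/0.65, 1/0.75, 1/0.85 and 1/0.95, that is by 54%, 33%, 18% and 5%. At r = 0.5, 42 unadjusted completers carry the information of 42 × 0.75 = 31.5 adjusted ones.

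**Cost of estimating the baseline coefficient.** A simulation of 20,000 trials with 42 patients, six equal groups, k = 1 and r = 0.5 gave a variance ratio for the dose slope of 0.775 against the theoretical 0.75. The cost is about 0.775/0.75 − 1 = 3%.

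**Illustrative power.** Suppose 76 completers would give the unadjusted slope test 80% power at two-sided 5% (an assumption, since the Protocol states no power). With the same effect and k = 1:

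| MDD completers | Unadjusted | Adjusted, r = 0.3 | r = 0.5 | r = 0.7 | r = 0.9 |
|---|---|---|---|---|---|
| 42 | 54% | 72% | 66% | 61% | 56% |
| 29 | 39% | 55% | 50% | 45% | 41% |

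**The case against.** Four objections carry weight.

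- **The covariate clause.** A reader might infer that the models exclude baseline. The text does not say so. Baseline HDRS-24 is a clinical covariate and can enter under the open clause, and covariate lists are often left to a SAP, which is not at hand. This limits the point to a missing commitment. It does not remove it, because the Protocol itself fixes the response and the only named predictor for three primary tests, and the clause binds the analyst to nothing.
- **Bias.** A reader might also infer that the dose slope is biased. Dose is randomised, so over repeated randomisations it is not. The loss is precision, plus sensitivity to whatever imbalance occurred in this sample. If dose enters as a single slope, the imbalance that counts is the baseline–dose correlation over all MDD patients, not differences between individual small groups.
- **Size.** The equal-SD column is favourable. The MADRS entry floor of 22 (Inclusion/Exclusion Criteria) may narrow the baseline spread of HDRS, and the pilot rise of more than 60% in glutamate and GABA (Lay Summary) may widen the follow-up spread. Either would push k above 1, where the gain can vanish. Where the residual ratio is 1.00, the cost of about 3% would leave adjustment very slightly worse. This stands, and it rules out quoting any single gain.
- **Timing.** Analysis is under way, so a covariate fixed now may not count as prespecified. This also stands and shapes the fix.

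Two further inferences lack support. Nothing in the Protocol says how large baseline measurement error is for edited MRS. And baseline values for all patients are the planned schedule; the number of usable baseline spectra is not reported.

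**Conclusion.** The point holds as a missing commitment. Aims 1–3 specify change on dose and do not commit to adjusting for scheduled pre-infusion values. Adjustment never has the larger residual variance and costs one degree of freedom.

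The benefit ranges from substantial (a ratio of 0.65 at r = 0.3 with equal SDs) to nil (1.00 at r = 0.7 with a follow-up SD 1.5 times baseline). The Protocol gives no r or SD with which to narrow that range. The small sample makes the point worth acting on: at most 55% of the required MDD completers, possibly 38%. The figure of 5 to 7 per group assumes equal allocation and rests on an unreported split of the 42 completers. If an existing SAP already names these covariates, the point is closed.

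**What to change.** Name the pre-infusion value of each outcome as a fixed covariate: pre-scan HDRS-24 in Aim 1, pre-infusion glutamate in Aim 2 and pre-infusion GABA in Aim 3. The response can stay as change, since with baseline in the model the dose coefficient is the same for change and for the follow-up value. Confine this to the randomised MDD dose comparison; the contrast of MDD patients with healthy volunteers in Exploratory Aim 1 is not randomised, and the argument does not carry over.

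Make the change before the dose models are run. If they have already been run, report both versions and label the adjusted one as added afterwards.

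The cost is one degree of freedom per model and a wording change. No new data are needed, but a patient without a usable pre-infusion value has no change score either, so adjustment loses no one further.

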Exploratory Aim 1: We hypothesize that the increase in the glutamate signal measured with MRS will be greater in depressed MDD patients compared with healthy non-depressed volunteers. We hypothesize a blunted GABA response in MDD. This hypothesis will be tested within separate linear model with change in (a) glutamate level and (b) GABA level as response, respectively. Predictors will include diagnosis and dose (for the MDD subjects), and other clinical and demographic covariates included as appropriate.

Description of Subject Population

Sample #1

Specify subject population

MDD Patients

Number of completers required to accomplish study aims

76

Projected number of subjects who will be enrolled to obtain required number of completers

120

Age range of subject population

18-65

Sample #2

Specify subject population

healthy volunteers

Number of completers required to accomplish study aims

10

Projected number of subjects who will be enrolled to obtain required number of completers

15

Age range of subject population

18-65

Gender, Racial and Ethnic Breakdown

No ethnic/racial/gender group is excluded. Estimate of gender and ethnic distribution of subject sample: Since subjects will be recruited in the same fashion as we have for previous studies, we expect that the sample will be similar to those who present currently to our program.

Gender: We expect more female representation as it reflects the general population where MDD is slightly more common in women

Ethnic: Of subjects who present to our clinic, approximately 15% are African-American, 20% are members of various Latino communities and the remainder are Caucasian.

Description of subject population

Subject population is MDD Patients and Healthy volunteers ages 18-65. No ethnic/racial/gender group is excluded.

Recruitment Procedures

Describe settings where recruitment will occur

Patients and healthy volunteers will be recruited through advertisement and patients may also come from referrals from private psychiatrists and clinics. Text of advertisements and other materials to be distributed in recruitment efforts will be submitted to the IRB for approval before they are distributed.

How and by whom will subjects be approached and/or recruited?

Subjects will be recruited through advertisements and referrals from private psychiatrists.

How will the study be advertised/publicized?

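### Exploratory Aim 1 enters dose only for MDD patients, so the diagnosis coefficient, read literally, compares MDD and control groups at different ketamine doses

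*Protocol*

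**What the plan says.** Specific Aims and Hypotheses, Exploratory Aim 1, gives two directional hypotheses. For glutamate, "the increase in the glutamate signal measured with MRS will be greater in depressed MDD patients compared with healthy non-depressed volunteers". For GABA, "We hypothesize a blunted GABA response in MDD". Each outcome gets its own linear model of change, and the predictors are named: "Predictors will include diagnosis and dose (for the MDD subjects), and other clinical and demographic covariates".

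The doses are set elsewhere in the protocol:

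- **Controls** (Study Procedures, Healthy Volunteers, MRS and MRI Scanning): all are scanned around a "slow intravenous infusion of saline solution with 0.5 mg/kg of ketamine hydrochloride". There is no other control dose and no control placebo.
- **Patients** (Study Procedures, Patients, Ketamine dosing): "Patients will be assigned to one of five ketamine doses or placebo". The dose values are in a figure that is not reproduced.
- **Top randomised dose** (Randomization and Partial Unblinding Process): the order-writing physician records "eligibility based on the randomization assignment as either 0.5 mg/kg of ketamine or less", so 0.5 mg/kg is the highest randomised dose. The 0.7 mg/kg option belongs to an open-label second infusion for which that section specifies no MRI, so it does not enter these data.

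Aims 2 and 3 hypothesise that glutamate and GABA rise with dose.

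**The concern.** The controls have a known, non-zero dose, and the stated predictor leaves it out. A diagnosis coefficient estimated beside an MDD-only dose term is a contrast at whatever dose value makes that term zero. With uncentred dose this is MDD on placebo; with dose centred at the patient mean it is MDD at the average dose. In both cases the comparator is controls at 0.5 mg/kg. Neither answers the question in the Lay Summary, which is how the glutamate and GABA responses to ketamine differ between MDD and healthy subjects.

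Under the protocol's own expectation that response rises with dose, both readings push the MDD effect down. For GABA that is the hypothesised direction, so a dose difference could be reported as blunting. For glutamate it runs against the hypothesis, so a real excess in MDD could be hidden or reversed. This comparison is the only use the aims make of the control group.

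**Working it through.** The protocol gives no SD, effect size or power for this aim, so there is no stated figure to reproduce. The algebra needs no assumed numbers; the illustration does.

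**1. What the coefficient estimates.** Let D be dose for MDD subjects and 0 for controls, and fit y = a + b·MDD + c·D. Then b = E[MDD at dose 0] − E[control at 0.5 mg/kg]. Suppose both groups share a linear dose response with slope s and there is no diagnosis difference:

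- control dose term zero: b = −0.5·s
- MDD dose centred at its mean m, controls 0: b = −(0.5 − m)·s
- actual dose for all, or MDD dose centred at 0.5 mg/kg: b = 0

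**2. The fit is the same under each coding.** Let A be the dose actually given. For everyone, A = D + 0.5·(1 − MDD). Substituting gives y = (a − 0.5c) + (b + 0.5c)·MDD + c·A. Fitted values and slope are identical; only the diagnosis coefficient moves, by 0.5c. The fault therefore lies in the dose at which the contrast is read.

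**3. Inputs for the illustration.**

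- From the protocol: 76 MDD and 10 control completers (Description of Subject Population); a pilot rise of more than 60% (Lay Summary).
- Assumed: that 60% applies at 0.5 mg/kg; linearity; doses 0, 0.1, 0.2, 0.3, 0.4, 0.5 mg/kg with near-equal allocation (13, 13, 13, 13, 12, 12); residual SD 30, 60 or 90 points; two-sided 5% test; no true diagnosis difference.

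**4. Bias.**

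- s = 60/0.5 = 120 points per mg/kg
- m = (13 × 0.6 + 12 × 0.9)/76 = 18.6/76 = 0.245
- zero coding: b = −0.5 × 120 = −60 points
- mean-centred: b = −(0.5 − 0.245) × 120 = about −30.6 points

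**5. False significance.** SE = SD × √(1/76 + 1/10 + (r − m)²/Sxx), with r the reference dose and Sxx = 2.188. The multipliers are 0.375 (r = 0), 0.336 (r = m) and 0.378 (r = 0.5). The rejection rates follow from the non-central t on 83 df:

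| SD (points) | Control term zero | MDD mean-centred | Contrast at 0.5 mg/kg |
|---|---|---|---|
| 30 | 100% | 85% | 5% |
| 60 | 75% | 32% | 5% |
| 90 | 42% | 17% | 5% |

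Simulation agrees to within about a point (41% and 16% in the last row). Under the first two codings virtually all these rejections are in the direction of a lower MDD response.

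**6. Sensitivity (simulation, SD 40 unless stated).**

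- Even grid: 97.7% (zero coding) and 60.5% (centred).
- Two skewed grids: 96.4% and 98.5% (zero); 40.3% and 79.7% (centred).
- 57 MDD and 13 controls, the numbers enrolled: 98.6% and 68.5%.
- 20% rise at 0.5 mg/kg, SD 30: bias −20 and −10 points; 42% and 18%.
- A saturating (Emax) dose response: bias −44 and −18 points; 82.1% and 24.2%. The linear contrast at 0.5 mg/kg then keeps about +9.5 points (8.1% rejection), while MDD at 0.5 mg/kg against controls stays unbiased (5.4%).
- No dose response: the bias vanishes (5.2% with zero coding).

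**7. Precision of the matched comparison.** With about 12 MDD patients at 0.5 mg/kg, SE = SD × √(1/12 + 1/10) = 0.428 × SD, against 0.378 × SD for the model contrast. That is a ratio of 1.13, so the SE is about 13% larger.

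**The case against.** The strongest reply is that nothing is mis-specified. The protocol does not say that controls are coded zero, that dose is centred at the patient mean, or that the raw diagnosis coefficient is the test. The parenthesis may only record that dose varies among patients alone. As step 2 shows, the named predictors already contain the contrast at 0.5 mg/kg, and a careful analyst would extract it. Coding is often left to the SAP, which is not at hand.

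Most of this stands, and it limits the point. A reader might infer that the model itself is wrong, or that the trial will report a false GABA result; the protocol supports neither. What remains is that it does specify a dose predictor, words it so as to leave out the controls' dose, and nowhere gives the dose at which diagnosis is compared. The literal reading and a common default (mean-centring) both give the wrong contrast.

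The objection also stands on size. The Lay Summary attaches no dose to the pilot rise, the dose grid is not shown, and no SD is given. Nor does reading the contrast at 0.5 mg/kg guarantee zero bias: that needs a linear dose response, whereas the rationale speaks of establishing a curve.

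**Conclusion.** The point holds as a defect in how the diagnosis contrast is defined. Read literally or with mean-centred dose, the coefficient compares MDD patients at placebo or at the average dose with controls at 0.5 mg/kg. The downward direction of the bias requires only that response rises with dose; it does not depend on the dose grid or the SD. The size (about −60 or −30 points, roughly 16% to 100% false significance) is an illustration resting on the assumed effect at 0.5 mg/kg, linearity, grid and SD.

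Severity is moderate. It would be tempting to treat this as undermining the trial's findings, but the aim is exploratory, only 10 control completers are planned, and primary Aims 1 to 4 use MDD patients alone and are untouched.

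**What to change.** State in Exploratory Aim 1 that the diagnosis contrast is evaluated at 0.5 mg/kg. Either enter the dose actually given for every subject, with controls at 0.5 mg/kg, or centre dose at 0.5 mg/kg; the two are equivalent. Because this is unbiased only if the dose response is correctly modelled as linear, also report MDD patients randomised to 0.5 mg/kg against controls for both glutamate and GABA, and comment if the two estimates differ.

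The cost is a line or two of model specification and one extra comparison, with no new data or patients. The matched comparison is somewhat less precise (SE about 13% larger on the assumed even grid). The continuation application reports that interventions are complete and only analysis is ongoing, so the change can still be made; it should be dated and identified as a clarification made at the analysis stage.
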